10.2. Pre-Screening

Prior to the Baseline/ Enrollment Visit, interested subjects will complete an online REDCap screening survey and have the opportunity to review the Informed Consent Forms (ICFs). After the successful

completion of the screening survey, the study staff will review the survey, and qualified subjects will be invited to attend a study Visit 1.

10.3. Subject Consent

At the enrollment visit, subjects will be approached to obtain written informed consent prior to any data collection. Once the Informed Consent Form (ICF) is collected, the screening of the subject will follow. The purpose of the study and the benefits and risks of the procedures will be explained to the subject, and the consent process must be documented. Subjects who agree to study participation must sign IRB- approved ICF. Consent to participate in this study must be given in writing. Subjects that are unable to give consent will not be included in the study.

The Investigator or designee must obtain written informed consent before any clinical study related activity takes place. Prior to entry into the study, the IRB and Medtronic-approved ICF form, and the Health Insurance Portability and Accountability Act (HIPAA) Authorization Form (if not included within the ICF) (the US only) will be given to each subject.

The Investigator or designee will fully inform the subject of all aspects of the clinical study that are relevant to the subject's decision to participate in the clinical study (e.g., purpose and duration of the study, requirements of the subject during the study, potential risks and possible benefits associated with participation in this study). All items addressed in the ICF must be explained. The language used shall be as non-technical as possible and must be understandable to the subjects. The subject must have ample time and opportunity to read and understand the ICF, to inquire about the details of the clinical study, and to decide whether or not to participate in the clinical study. All questions about the clinical study should be answered to the satisfaction of the subject. In the case that a subject is unable to read, an impartial witness must also be present and sign the informed consent to confirm that the research has been clearly explained and all of the subject's questions have been answered.

Neither the Investigator nor the investigation site staff shall coerce or unduly influence a subject to participate or to continue to participate in the clinical study. The informed consent process shall not waive or appear to waive the subject's rights. When the subject decides to participate in the clinical study, the HIPAA Form (if applicable) and the ICF must be personally signed and dated by the subject.

After the subject has signed and dated the ICF, the Investigator must provide the subject with a copy.

Medtronic will inform the Investigators whenever information becomes available that may be relevant to the subject's confirmed participation in the clinical study. The Investigator or his/her authorized designee should inform the subject in a timely manner.

Medtronic will revise the written ICF whenever new information becomes available that may be relevant to the subject's confirmed participation in the clinical study. The revised information will be sent to the Investigator for approval by the IRB. After approval by the IRB, a copy of this information must be provided to the participating subjects, and the informed consent process, as described above, needs to be repeated.

10.4. Baseline/ Enrollment - Visit 1

After successful completion of the pre-screening, qualified subjects will be invited to attend Visit 1 to complete the ICF. The Investigator or designee will inform the prospective subjects on the study procedures and explain the consenting process. Once ICF is signed, the following will be performed during the screening:

- Demographics (race, ethnicity, sex, height, weight, skin tone, calculated body mass index (BMI)) will be recorded on the eCRFs;
- Medical History will be evaluated and documented to evaluate for prior or existing medical conditions and/or procedures that would exclude subjects from participation in the study;
- Physical examination including an evaluation of general appearance, cardiovascular, respiratory musculoskeletal system, skin, neurologic function, and head, eyes, ears, nose, and throat; The American Society of Anesthesiologist (ASA) physical status classification system is used to evaluate the degree of a patient's "sickness" or "physical state." Only subjects with ASA Physical status 1 will be enrolled;
- Concomitant Medications, including the history of prescription and over the counter medication, will be carefully noted and recorded. Medication name, indication for use, dose, frequency, route of administration start/stop date will be recorded on the eCRFs;
- Vital signs - Heart Rate, Systolic, and Diastolic Blood Pressures, Respiratory Rate and Oxygen Saturation (SpO₂) will be evaluated and recorded;
- Single 12-lead ECG;
- Complete blood count (CBC);
- Urinary pregnancy test;
- A urine sample will be tested for the presence of cotinine (nicotine metabolite) to exclude smokers;
- Female subjects will have to attest to birth control methods;

- Adverse event review will be completed to assess events the baseline, and that occur after enrollment.

The **Baseline/ Enrollment** results will stay valid for **60 days**.

10.5. Execution – Visit 2

10.5.1. Prior to Procedure

On the study day, subjects will arrive at the clinical research unit with appropriate fluid and solid intake as directed by study staff. The subject will be instructed not to consume beverages and foods containing alcohol, grapefruit, or caffeine/xanthine from 48 hours before dosing until the end-of-study visit. All subjects will fast as it will be instructed by the Investigator or designee before the start of the drug administration. The per dosing instructions will be provided to the subject.

- Any significant change in health status since Visit 1 will be recorded.
- Concomitant Medication and adverse events will be checked.
- All subjects will have urine drug screen and alcohol breathalyzer (Oral Ethanol) tests done.
- Female subjects, childbearing age, will also have a urine pregnancy test done.
- Review Inclusion and Exclusion Criteria based on additional information.
- Enrollment is based upon successful inclusion /exclusion criteria during Visits 1 and 2.

10.5.2. Procedure – Visit 2 and Visit 3

[figure not shown]

Figure 5: Schematic Representation of Procedure Schedule

The subjects will receive two regimens of anesthesia with different drug combinations, with at least a 1-week washout period between regimens. Once the pre-procedure part completed, the subject will be sequentially assigned to start with either Propofol (P) or Propofol with 4 ng/ml of Remifentanil (R) regimens, as shown in Figure 5.

10.5.2.1. Safety Monitoring

For the subject's safety, an anesthesiologist authorized to administer sedation drugs will be responsible for administering any procedural drugs for the sedation and monitoring of subject safety and physical state. All other personnel involved with the safety monitoring of subjects must be trained in and familiar with the management of recovery of sedated patients. The study site should have a setting that is fully equipped for the monitoring and support of the respiratory and cardiovascular function. Subjects will be continuously monitored throughout the study. All subjects will be monitored using an electrocardiogram (ECG), Pulse Oximeter for SpO₂, EtCO₂. A clinician will be monitoring respiratory and cardiac functions to determine if interventions are needed to maintain an adequate airway. The respiration support will be provided to ensure an unobstructed airway, adequate oxygenation (SpO₂ >92%), and CO₂ homeostasis throughout the study. As needed for airway support, the anesthesiologist may gently lift chin or jaw thrust (with or without manually assisted breathing), insertion of an airway device (oropharyngeal airway or laryngeal mask airway) and/or intermittent positive pressure ventilation (IPPV). Mask or nasal cannula will be used for supplemental O₂ delivery.

Any study procedures may be discontinued for the subject's safety. For patient safety, modifications to the procedure steps will be left to the judgment of the Principal Investigator.

10.5.2.2. Regimen Set-Up

The propofol and remifentanil will be administered using the Total Intravenous Anesthesia (TIVA) method via the target-controlled infusion (TCI) computer-controlled program, e.g., TIVA Trainer, or another computer-controlled program, to ensure that the targeted effect-site concentration of a drug is reached and maintained at each drug concentration plateau. 1% propofol and remifentanil diluted to a single concentration of 50 µg/ml will be used for this study. The infusion rate between 0 and 1200 ml/hr will be used to achieve a targeted concentration of propofol and remifentanil. For propofol, the effect-site concentration for propofol will be predicted using Schneider pharmacokinetics and pharmacodynamics (PK/PD) model [45, 46]. For remifentanil, Minto [47, 50] PK/PD model will be used. The assisted ventilation of the subject with either facemask, LMA or intermittent positive pressure ventilation (IPPV) may be used.

Subjects will have an intravenous catheter inserted for fluid and drug administration. Blood pressure will be monitored using an automated blood pressure cuff.

10.5.2.3. Sensor Application

The BIS™ sensor will be applied per its IFU. Subjects will have an intravenous catheter inserted for fluid and drug administration. The TES sensor will be applied per its IFU to the calf with a stimulation of 2mA, 2Hz for 1-5 seconds provided to ensure proper application.

The subject will rest for ~12 minutes before starting any regimen.

MOAA/S and Tetanic Electrical Stimulation (TES)

At each steady-state step and after equilibration, the MOAA/S assessment will be administered by an anesthesiologist. It is preferred that the same anesthesiologist performs the MOAA/S assessment for all subjects, refer to **Appendix A**.

Subjects will receive noxious electrical stimulation using Tetanic Electrical Stimulation (TES) once they achieve a MOAA/S score <2. The instructions for testing the sensor placement are listed above. The BIS™ value will be recorded, followed by the MOAA/S assessment. Then, TES will be initiated following the Instructions for Use (IFU) for the XAVANT STIMPOD™ NMS 410/450X device. The subject will receive one stimulation of 50mA, 50 Hz for 5 seconds. Their response, such as withdrawal of the extremity, a facial grimace, or a verbal groan will be recorded. Approximately 2 minutes after this assessment, the BIS™ value will be recorded.

10.5.2.4. Propofol Group

The initial target effect-site concentrations of propofol will be 0.5 µg/ml followed by incremental increases in the target effect-site concentrations of 1.5, 2, 2.5, 3, 4, 6, to a maximum of 8 µg/ml until a BIS™ value of not lower than 30 is intentionally reached or per Investigator's discretion. The BIS™ value should not intentionally be taken below 30. The equilibration time for each targeted plateau will be at least 12 minutes. The BIS™ value and MOAA/S score will be assessed and recorded when the patient is awake and at the different targeted propofol concentrations. Tetanic Electrical Stimulation (TES) will be used following the MOAA/S assessment when the subject reaches a MOAA/S score of <2. The BIS™ value will be recorded at the time of subject's response and approximately 2 minutes following the TES assessment. The propofol concentration will be decreased by the same steps until consciousness occurred.

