Study Design	This is a single-center, prospective, non-randomized, cross-over study to collect data to evaluate the relationship between BIS™ and anesthetic regimens. The subjects will receive two regimens of anesthesia with different drug combinations, with at least a 1-week washout period between regimens. Subjects will be sequentially assigned to start with either Propofol (P) or Propofol with 4 ng/ml of Remifentanyl (R) regimens with the BIS™ bilateral sensor placed on the subject's forehead. The Modified Observer's Assessment of Alertness/Sedation (MOAA/S) scale will be used to measure the level of alertness in sedated subjects, with Tetanic Electrical Stimulation (TES) being used once the patient is unresponsive to tactile stimuli (e.g., MOAA/S < 2). The loss of tactile stimulus response will be defined according to the MOAA/S score value <2.

Medtronic Controlled Information

Clinical Investigation Plan

[figure not shown]
SONORA

MDT19049SONORA

Version 5.0

Page 11 of 75

Medtronic

	
TES will then be initiated once the subject reaches an MOAA/S <2, with a one-time stimulation of 50mA, 50 Hz delivered for 5 seconds. The subject's response will be recorded along with the BIS™ value prior to stimulation, at the time of stimulation and 2 minutes following stimulation. The data will be used to gauge the influence of stimulation on the subject's level of sedation, pre-TES and post-TES.
 
Sample Size	
To collect 20 complete data sets, up to 30 subjects will be enrolled to account for anticipated screen failures and subject dropouts. Based on the dose-response Hill equation with an allowable error of $\pm 15\%$ for BIS₅₀ and coefficient of variation of 25% at the alpha level of 0.05, the sample size will provide sufficient power (>80%) to evaluate the performance of anesthetic agents/ regimens.

Duration	
The study duration is expected to be up to approximately 4 months. The expected duration of each subject will be approximately (~) 10 hours. The Enrollment Visit should take approximately 2 hours to complete, and each Study Visit will be approximately 4 hours per subject. Each subject will be contacted by phone within 48 hours of the study participation.

Planned number of sites	
1 site in the US

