- The propofol and remifentanyl will be administered using the target-controlled infusion (TCI) computer-controlled program, e.g., TIVA Trainer, or another computer-controlled program/pump, to ensure that the targeted effect-site concentration of a drug is reached and maintained at each drug concentration plateau
- 1% propofol and remifentanyl diluted to a single concentration of 50 µg/ml will be used for this study. Infusion rate between 0 and 1200 ml/hr. will be used to achieve a target effect-site concentration of propofol and remifentanyl
- For propofol, the effect-site concentration for propofol will be predicted using Schneider pharmacokinetics and pharmacodynamics (PK/PD) model, and for remifentanyl, Minto PK/PD model will be used

- The assisted ventilation of the subject with either facemask or LMA may be used.
- Each subject will receive one of the anesthetic regimens. The subject will rest for ~ 15 minutes before starting any regimen
- MOAA/S Assessment
- Once subjects reach a MOAA/S score of <2, they will receive noxious electrical stimulation using Tetanic Electrical Stimulation (TES). The BIS™ value will be recorded, followed by the MOAA/S assessment. Then, TES will be initiated with one stimulation to the tibial nerve at 50mA, 50Hz for 5 seconds. The subject's pain avoidance behavior, such as withdrawal of extremity, facial grimace or verbal groan, will be noted. The BIS™ value will then be recorded at the time of subject's response and 2 minutes following the TES assessment
- Adverse Event Assessment
- Device Deficiency Assessment

A clinician will be monitoring respiratory and cardiac functions to determine if interventions are needed to maintain an adequate airway. The respiration support will be provided to ensure an unobstructed airway, adequate oxygenation (SpO₂ >92%), and CO₂ homeostasis throughout the study. As needed for airway support, the anesthesiologist may gently lift chin or jaw thrust (with or without manually assisted breathing), insertion of an airway device (oropharyngeal airway or laryngeal mask airway) and/or intermittent positive pressure ventilation (IPPV). Mask or nasal cannula will be used for supplemental O₂ delivery.

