	
For the Propofol with Remifentanil group, where remifentanil is administered with propofol, approximately 2 minutes before starting propofol, to attain an effect-site targeted concentration of remifentanil of 4 ng/ml, remifentanil will be given by a continuous infusion. Within approximately 7 minutes, the infusion rate of Remifentanil may be adjusted to maintain the effect-site concentration of remifentanil of 4 ng/ml throughout the study. The equilibration time for each targeted plateau will be approximately 12 minutes. The BIS™ value and MOAA/S scale will be assessed when the patient is awake and at different propofol concentrations. TES will then be initiated following the MOAA/S assessment once the subject reaches a MOAA/S <2. The BIS™ value will be recorded approximately 2 minutes following the TES assessment.
 
The cardiac output will be monitored, and subjects could be discontinued per PI's discretion. The respiratory rate will be monitored, a respiratory rate of 4 breaths/minute or less will be considered evidence of respiratory toxicity, and remifentanil will be discontinued.
 
The start time of any drug infusion, target effect-site concentrations and infusion rate will be noted in the electronic Case Report Forms (eCRFs). The BIS™ value prior to MOAA/S assessment and TES will be noted along with the BIS™ value at the time of subject's response and 2 minutes following the TES assessment. Any adjustments to the infusion rate and time of adjustment as well as any changes to the subject management during the procedure will be recorded.
 
The device data (raw signals), including Heart Rate, Blood Pressure, Respiration Rate, EtCO₂, SpO₂, BIS™, TCI, if available, will be recorded in real-time during the procedure and files will be provided to Medtronic by the site. The instructions on the secure data transfer will be provided by Medtronic.
 
Each subject will be contacted by phone within 48 hours after completion of the procedure to perform a safety assessment

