10.5.2.6. CRF Data Collection

The start time of any drug infusion, target effect-site concentrations, infusion rate, the start time of the assessments including BIS™ value prior to MOAA/S assessment, Tetanic Electrical Stimulation (TES) and the end time of assessment as well as the BIS™ value at the time of subject's response and approximately 2 minutes following the TES assessment will be recorded in the electronic Case Report Forms (eCRFs). Any adjustments to the infusion rate and time of adjustment will be recorded, and any changes to subject management during the procedure will be noted on the eCRFs.

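### The immediate BIS reading around TES has no single time anchor and, under the eCRF wording, no defined time for a subject who does not respond

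*Protocol*

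**What the plan says.** The protocol times the immediate reading in different ways in its current text.

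- **At the stimulus.** The synopsis, Study Design row, says: "The subject's response will be recorded along with the BIS™ value prior to stimulation, at the time of stimulation and 2 minutes following stimulation". It also states the purpose: "The data will be used to gauge the influence of stimulation on the subject's level of sedation, pre-TES and post-TES".
- **When the subject responds.** The Procedure Assessments bullets of the synopsis say: "The BIS™ value will then be recorded at the time of subject's response and 2 minutes following the TES assessment". The synopsis paragraph for the Propofol group agrees, as do 10.5.2.4 ("The BIS™ value will be recorded at the time of subject's response and approximately 2 minutes following the TES assessment") and 10.5.2.5. The eCRF list in 10.5.2.6 requires that "the BIS™ value at the time of subject's response and approximately 2 minutes following the TES assessment will be recorded".
- **No immediate reading.** The general TES procedure in 10.5.2.3 has a BIS value before the MOAA/S assessment and then only this: "Approximately 2 minutes after this assessment, the BIS™ value will be recorded".

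The synopsis paragraph for Propofol with Remifentanil mentions only the later reading ("The BIS™ value will be recorded approximately 2 minutes following the TES assessment"). A data-recording paragraph further down the same synopsis entry, not limited to one regimen, restores the reading at the response.

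Section 10.5.2.3 describes the response by examples of behaviour: withdrawing the limb, grimacing or groaning. No section says what to enter when none of these occurs.

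**The concern.** TES is given only once MOAA/S is below 2, and propofol targets may rise to 8 µg/ml, in one regimen with remifentanil. Some subjects may therefore show no behavioural response, although the documents give no rate. Under the eCRF wording, staff would either leave the immediate field blank for these subjects or choose a time themselves.

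In the first case, whether the value exists depends on the reaction to the stimulus, which is closely tied to the effect the synopsis wants to gauge. In the second, the reading has no common meaning across subjects. Either way, the immediate BIS change cannot be read as the average effect of TES in those who received it. A site also cannot follow the synopsis Study Design row, 10.5.2.3 and 10.5.2.4 all at once.

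**Working it through.** **Step 1. The passages side by side.**

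| Place in the protocol | Before TES | Immediate | About 2 min after |
|---|---|---|---|
| Synopsis, Study Design | yes | at the stimulus | yes |
| Synopsis, Procedure Assessments bullets | yes, before MOAA/S | when the subject responds | yes |
| Synopsis, Propofol paragraph | BIS at each concentration | when the subject responds | yes |
| Synopsis, Propofol with Remifentanil paragraph | BIS at each concentration | not mentioned | yes |
| Synopsis, data-recording paragraph | yes | when the subject responds | yes |
| 10.5.2.3 | yes, before MOAA/S | none | yes |
| 10.5.2.4 and 10.5.2.5 | BIS at each concentration | when the subject responds | yes |
| 10.5.2.6 (eCRF) | yes | when the subject responds | yes |

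The first and last columns do not depend on a response. Only the middle column does, and only there do the passages conflict.

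**Step 2. Who has a value.** Read literally, 10.5.2.6 gives every stimulated subject a reading before TES and one about 2 minutes after. The immediate reading exists for responders only.

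**Step 3. Size of the bias in that field.** The plan has no figure to reproduce here. Let R and N be the mean immediate BIS change in responders and non-responders, D = R - N, and p the share responding.

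- Mean over all stimulated subjects: pR + (1-p)N.
- Mean from the responder-only field: R.
- Overstatement: R - pR - (1-p)N = (1-p)(R - N) = (1-p) x D.

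Neither p nor D is in the documents, so the values below are assumptions. The count uses the planned 20 subjects (14.1) with one TES each, for simplicity.

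| p | Immediate readings out of 20 | D = 5 | D = 10 | D = 15 |
|---|---|---|---|---|
| 0.2 | 20 x 0.2 = 4 | 0.8 x 5 = 4 | 8 | 12 |
| 0.5 | 20 x 0.5 = 10 | 0.5 x 5 = 2.5 | 5 | 7.5 |
| 0.8 | 20 x 0.8 = 16 | 0.2 x 5 = 1 | 2 | 3 |

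If D were 0, there would be no bias in the mean, only missing values.

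**Step 4. What else depends on this field.** BIS50, BIS95 and Pk (Protocol 5.1 and 14.3, SAP 7.2.1) classify subjects by MOAA/S score, not by response to TES. TES is in no primary or secondary objective. The SAP states that it is based on CIP Version 1 and contains no TES analysis.

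**Step 5. Whether the value can be recovered.** Section 10.5.2.7 records BIS in real time, 10.5.2.6 records assessment times including TES, and 10.11 lists missing raw BIS data as an example of a major deviation. So a value at a fixed time from TES could be extracted for every subject. No section plans this or sets the time, and 16.1 says raw device data will not be monitored.

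**The case against.** The best defence is that the wording is loose rather than wrong. TES is a single 5-second stimulus, and the Study Design row pairs the response with the BIS readings. The time of response could therefore mean the moment at which the response is judged, including a judgement of none. The continuous record also means that nothing is lost for good, and no planned estimate uses the field.

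Much of this stands. It limits the consequences, and it makes the responder-only rule a literal reading rather than a certain one. It does not remove the conflict with 10.5.2.3, which has no immediate reading at all. Nor does it tell staff when to read the monitor if nothing happens. Without a time set in advance, values taken from the log later would rest on a time chosen after the data were seen.

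A reader might infer more than the documents support:

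- *That the whole TES effect on BIS is measured in responders only.* It is not. The readings before TES and at 2 minutes exist for all stimulated subjects and support a pre/post comparison.
- *That the synopsis drops the immediate reading for the remifentanil regimen.* Its regimen paragraph is silent, but the later data-recording paragraph and 10.5.2.5 include the reading.
- *That the synopsis as a whole uses the stimulus as anchor.* Only the Study Design row does.
- *That a real difference between regimens would be hidden.* No such TES comparison is planned, and no response rates are given from which to judge it.
- *That a grimace corrupts the reading.* Protocol 4.1.2 says BIS values assume an EEG free of artifacts, but 7.1 says the BISx4 unit analyses the signal for artifact. A fixed reading soon after TES could meet the same movement.

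**Conclusion.** The concern holds for one reading. The immediate BIS value around TES is timed inconsistently, and under the literal eCRF rule it has no defined time for a subject who does not respond. An analysis of that field would then be selected on response and would overstate the average immediate change by (1-p) x D when D is positive. That is 1 to 12 BIS points over the assumed range in the working; the true size is unknown.

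The consequence is confined to the exploratory use of the TES data stated in the synopsis Study Design row. The primary and secondary estimates are not affected, and the missing values could be recovered from the device files if TES times and raw data are complete. This should be corrected, because the correction is cheap, but it does not threaten the study's main results.

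**What to change.** Reconcile the synopsis (Study Design row, Procedure Assessments bullets, both regimen paragraphs and the data-recording paragraph), sections 10.5.2.3 to 10.5.2.6 and the eCRF to one schedule tied to the stimulus:

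1. BIS immediately before TES. Section 10.5.2.3 takes the earlier value before MOAA/S, and the lowest MOAA/S scores involve a painful trapezius squeeze (Appendix A). A value just before TES keeps that stimulus out of the interval.
2. BIS at one fixed time from TES onset, set in advance.
3. BIS about 2 minutes after TES, as now.

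Apply this to every TES in both regimens, whether or not the subject responds. Record response yes/no, and its time if any, as separate eCRF fields. Take the fixed-time value from the real-time BIS record (10.5.2.7) using the recorded TES time, which must be on the same clock as the BIS monitor.

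The cost is minor: protocol and eCRF wording, plus data extraction from files already collected. No procedure is added. Subjects already studied can be handled the same way where the TES time and raw BIS file are available.
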